#### 9.1.1 Severity

Severity of an adverse event is defined as a qualitative assessment of the degree of intensity of an adverse event as determined by the investigator or reported to him/her by the patient/subject. The assessment of severity is made

irrespective of relationship to investigational product or seriousness of the event and should be evaluated according to the following scale:

- *Mild*: Event is noticeable to the subject, but is easily tolerated and does not interfere with the subject's daily activities.
- *Moderate*: Event is bothersome, possibly requiring additional therapy, and may interfere with the subject's daily activities.
- *Severe*: Event is intolerable, necessitates additional therapy or alteration of therapy, and interferes with the subject's daily activities.

#### 9.1.2 Relationship to Investigational Product

The relationship of each adverse event to the investigational product should be determined by the investigator using these explanations:

- *Related*: A reasonable possibility exists that the investigational product caused the adverse event.
- *Not Related*: A reasonable possibility does not exist that the investigational product caused the adverse event.

## 9.2 Serious Adverse Events

An adverse event is considered to be serious if, in the view of the investigator it results in any of the following outcomes at any dose of IMP:

- Death;
- A life-threatening or places the participant at immediate risk of death from the event as it occurred;
- Inpatient hospitalization or prolongation of existing hospitalization;
  - Note: The term “inpatient hospitalization” refers to any hospital admission (even if less than 24 hours). Planned hospitalization for pre-existing condition without a serious deterioration in health, is not considered to be a serious adverse event.
  - Note: The term “prolongation of existing hospitalization” refers to any extension of an inpatient hospitalization beyond the stay anticipated or required for the reason for the initial admission as determined by the investigator or treating physician.
- A persistent or significant disability, incapacity or substantial disruption of the ability to conduct normal life functions;

- Note: A serious adverse event specifically related to visual threat would be interpreted as any potential impairment or damage to the subject's eyes (e.g., hemorrhage, retinal detachment, central corneal ulcer or damage to the optic nerve).
- A congenital anomaly/birth defect.

Important medical events that may not result in death, are life-threatening, or require hospitalization may be considered serious when, based upon appropriate medical judgment, they may jeopardize the patient or subject and may require medical or surgical intervention to prevent one of the outcomes listed in this definition.

### **9.3 Procedures for Reporting Adverse Events**

All adverse events and their outcomes must be reported to IRW.

#### **9.3.1 Reporting a Serious Adverse Event (SAE)**

All SAEs must be reported by the Investigator using phone or email or fax within 24 hours of knowledge of the event to the Monitor or other members of the staff at IRW, regardless of the time that may have elapsed from the time the event occurred to when the Investigator first learns of it. The Initial Report should contain as much information as possible, but a minimum the following information:

- \* subject identification
- \* treatment specification (blinded information, if code not broken)
- \* adverse event diagnosis
- \* time specification for the medical event
- \* name of the original reporter

A Serious Adverse Event Report Form must also be completed, signed by the Investigator and submitted to IRW no later than 24 hours after the initial information was received. Apart from the information above, this Follow-up Report should also contain the following information:

- \* assessment of severity
- \* assessment of causality

No distinction should be made between the investigational product or reference/placebo product regarding reporting of SAEs as long as the code is not broken.

SAEs should be reported to IRW even after the clinical trial has been finished, if, in the judgment of the Investigator, there might be an association between the event and the previous use of the IMP or as a result of the trial procedures.

The contact details of the safety team and reporting procedure are described in the separate Safety Manuals (Site and Sponsor/CRO obligations).

#### **9.3.2 Reporting a Suspected Unexpected Adverse Reaction (SUSAR)**

Only SAEs that are both unexpected and related to the investigational product, Suspected Unexpected Serious Adverse Reactions (SUSARs), are subject to expedited reporting to the respective CA and IEC.

IRW is responsible for informing all Investigators concerned of relevant information about SUSARs that could adversely affect the safety of subjects. The appropriate IEC and CA as per local requirements, should be informed by IRW about SAEs associated with the use of the product (SUSARs).

### **9.4 Procedures for Unmasking (if applicable)**

Investigators will be provided with emergency code-break envelopes for all subjects and a complete set of emergency code-break envelopes will be retained by IRW.

Breaking the code must only be done in medical emergency situations and should only be used when knowledge of the treatment is necessary for the proper management of the subject. If the treatment code envelopes are broken, the reason and the date should be recorded on the envelopes and signed by the Investigator. Decoding of the blinded treatment must be reported to IRW and Oculis as soon as possible.

### **9.5 Type and Duration of the Follow-up of Subjects after Adverse Events**

If a trial Subject is withdrawn due to an AE, or if an AE persists at the end of the trial treatment period, this should be followed up until the condition has ceased or until the subject is under professional medical care and a potential causality between the investigational product and the AE has been penetrated. An outcome assessment should be performed when an AE persists.

### **9.6 Periodic Safety Reporting**

During the course of the trial, annual safety reports (DSUR) should be sent to the Competent Authority and IEC, as applicable. The reporting time frame for annual reports starts with the date of the first authorization by a Competent Authority.

## 10 STATISTICAL HYPOTHESES AND METHODS OF ANALYSES

### 10.1 Study Endpoints

#### 10.1.1 Primary Efficacy Endpoints

- Mean change in ETDRS BCVA letters at Week 12 compared to baseline

#### 10.1.2 Secondary Efficacy Endpoints

- Mean change in ETDRS BCVA letters at Weeks 2, 4, 8, and 16 compared to baseline
- Mean ETDRS BCVA letters at Weeks 2, 4, 8, 12, and 16
- Proportion of subjects with  $\geq 10$  and  $\geq 15$  ETDRS BCVA letter improvements from baseline.
- Proportion of subjects reaching 20/20 vision at week 12
- Proportion of subjects with  $\geq 15$  ETDRS BCVA letter loss from baseline.
- Mean change in central macular thickness (CMT) as assessed by SD-OCT at Weeks 2, 4, 8, 12, and 16 compared to baseline
- Mean CMT as assessed by SD-OCT at Weeks 2, 4, 8, 12, and 16
- Quality of life as assessed at week 12 by NEI VFQ-25

#### 10.1.3 Safety Endpoints

- Adverse Events
- Safety laboratory tests: biochemistry and hematology
- Intraocular pressure
- Slit lamp biomicroscopy
- Dilated Indirect Ophthalmoscopy

### 10.2 Hypotheses

The statistical hypotheses for the primary endpoint of mean change from baseline BCVA ETDRS letters in the study eye at Week 12 are as follows:

$H_0$ : The difference between study eyes treated with DexNP and study eyes treated with Vehicle (DexNP – Vehicle) in the mean change from baseline ETDRS BCVA letters to Week 12 (Week 12 – Baseline)  $\leq 0$ .

$H_1$ : The difference between study eyes treated with DexNP and study eyes treated with Vehicle (DexNP – Vehicle) in the mean change from baseline ETDRS BCVA letters to Week 12 (Week 12 – Baseline)  $> 0$ .

The study will be considered a success if  $H_0$  is rejected in favor of  $H_1$  and superiority of DexNP to Vehicle is claimed.

### **10.3 Sample Size**

Assuming a difference in the mean change from baseline ETDRS BCVA to Week 12 of 3.5 letters between DexNP and vehicle, a common standard deviation in the change from baseline ETDRS BCVA letters to Week 12 of 8 letters within each treatment group, an overall 1-sided alpha = 0.15, a 2:1 randomization, and an interim analysis when 50% of the subjects complete Week 12 using an O'Brien-Fleming alpha spending function, 58 DexNP and 29 Vehicle subjects (study eyes) are required to have 80% power to reject the null hypothesis. Assuming 10% discontinuation rate, a total of 96 subjects will be randomized.

### **10.4 Interim Analysis**

An interim analysis will be conducted by an independent biostatistician (to avoid introducing an operational bias) when approximately 50% of the subjects (44 subjects) complete Week 12. Statistical inference at the interim will be made at a 1-sided alpha = 0.04177. Statistical inference at the final analysis will be made at a 1-sided alpha = 0.13793. While there is no plan to stop early for a claim of superiority the O'Brien-Fleming boundary will serve to mitigate any concerns about that possibility and impacts overall power only minimally. If the interim is completed when precisely 50% of the subjects complete the trial through Week 12, the hypotheses will be tested using an efficacy boundary of 1.73051, corresponding to a one-sided alpha of 0.04177 at the interim analysis and using an efficacy boundary of 1.08968, corresponding to a one-sided alpha of 0.13793 at the final analysis. Note the actual boundaries will be calculated based on the percent of information used in the interim analyses.

No other study personnel other than the designated unmasked statistician and SAS programmers will be unmasked to the individual subject treatment assignments at the interim analysis. Additionally, a person appointed by the sponsor will be unmasked to treatment group summaries.

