### **10.5 Study Populations**

*ITT Population:* The intent-to-treat (ITT) population will consist of all randomized subjects, analyzing subjects under the treatment to which they were randomized.

*PP Population:* The per-protocol (PP) population is a subset of the ITT population and includes subjects who do not deviate from the protocol in any way likely to seriously affect the primary outcome of the study, analyzing subjects under the treatment actually received. Important protocol deviations related to study inclusion or exclusion criteria,

conduct of the trial, subject management, or subject assessment will be identified prior to unmasking treatment.

*Safety Population:* The safety population includes all randomized subjects who receive at least one dose of study medication. The safety population will be analyzed as treated and will be used for the safety analyses. No data will be excluded for any reason.

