#### 10.6.4 Secondary Efficacy Analyses

Change from baseline in ETDRS BCVA letters to Weeks 2, 4, 8, and 16 and ETDRS BCVA letters at Weeks 2, 4, 8, 12, and 16 will be analyzed similarly to the primary efficacy analyses using ODO on the ITT population.

Mean and mean change in central retinal subfield thickness will be analyzed similarly to ETDRS BCVA.

The proportion of study eyes a) gaining at least 10 or 15 letters BCVA and b) losing at least 15 letters will be summarized using discrete summary statistics. Treatment comparisons will be completed using Pearson's chi-squared statistic, with Fisher's exact statistic used for any comparison with an expected cell frequency of 5 or less. Confidence intervals (70%, 90%, and 95%) will also be presented for each treatment group and the difference between treatment groups, using asymptotic or exact methodology as consistent with the employed testing procedure. The analyses will be completed primarily on the ITT population and secondarily on the PP populations using ODO.

In all of these analyses, data from subject visits after receipt of rescue medication will be imputed using last observation prior to receiving rescue medication for continuous endpoints and will be imputed as failures for success/failure variables.

The VFQ-25 measurements will be summarized using continuous summary statistics for the total score, subscale scores, and each individual question score using observed data only. Imputation of missing individual question scores in calculating subscale and total scores will be detailed in the formal statistical analysis plan and will follow methodology used in developing the instrument.

One-sample t-tests will be used to primarily analyze the mean change from baseline within a treatment group; additionally, the non-parametric Wilcoxon signed-rank test will be used secondarily to analyze the change from baseline. Two-sample t-tests will be used to primarily analyze the difference in the mean scores between treatments at each visit and change from baseline; additionally, the non-parametric Wilcoxon rank-sum test will be used secondarily to analyze the differences in scores between treatments.

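### Section 10.4 gives arm-level interim results to a sponsor appointee with no stated purpose, decision or separation from trial conduct, which weakens the plan's own safeguard against operational bias

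*Combined protocol and SAP*

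**What the plan says.** Section 10.4 begins: "An interim analysis will be conducted by an independent biostatistician (to avoid introducing an operational bias", with the look set at about 44 subjects with Week 12 data. On decisions it says only: "While there is no plan to stop early for a claim of superiority". The O'Brien-Fleming boundary is kept to cover that possibility.

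The section then sets access at two levels. Individual assignments go to the unmasked statistician and the SAS programmers only. Arm-level results go further: "Additionally, a person appointed by the sponsor will be unmasked to treatment group summaries".

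Four other places bear on what could still be influenced after the look:

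- Section 10.5 defines the per-protocol set through important deviations. Those related to eligibility, "conduct of the trial, subject management, or subject assessment will be identified prior to unmasking treatment".
- Section 10.6.3 bases the primary analysis on multiple imputation with a pattern mixture model. It does not give the model, the assumptions about missing values or the number of imputations.
- Section 8.7 lets the sponsor end the study at any time, given notice. It sets no criteria.
- Section 5.1 plans about 13 sites recruiting 2 to 5 patients each per month.

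The documents describe no futility rule, sample-size re-estimation, data monitoring committee, charter or firewall.

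**The concern.** An independent statistician protects a trial by keeping comparative results away from people who can still affect it. Restricting the individual codes is not enough for this, because operational bias can arise from knowing the size and direction of the difference without knowing any one subject's arm. Section 10.4 writes in a permission that cuts across its own safeguard, and nothing elsewhere reconciles the two.

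If the recipient had a working role in the trial, that knowledge could colour follow-up effort and data queries, the classification of deviations, the details of the primary imputation, or a decision to stop under Section 8.7. It is also unclear whether deviations classified after this disclosure would still meet the Section 10.5 condition that they be identified before unmasking.

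**Working it through.** **1. Reproduce the plan's interim design.** Section 10.3 gives "an overall 1-sided alpha = 0.15", a 3.5-letter difference, an SD of 8, 2:1 allocation, and 58 and 29 evaluable subjects.

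- Interim alpha at half the information: 2 × [1 − Φ(z(0.925)/√0.5)] = 0.04177, boundary 1.73051. This matches the plan.
- Final boundary, from the bivariate normal with correlation √0.5: 1.0897 (one-sided alpha 0.1379). The plan has 1.08968 and 0.13793.
- Overall alpha with the stated boundaries: 0.1500.
- Drift: 3.5 / (8 × √(1/58 + 1/29)) = 3.5 / 1.819 = 1.924. Group-sequential power is 80.6%, against the stated 80%.

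The design figures hold. The point concerns access only.

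**2. How much the summaries tell the recipient.** With 44 subjects at 2:1 (29.33 and 14.67), the standard error of the difference is 8 × √(1/29.33 + 1/14.67) = 2.56 letters, and Z1 = difference / 2.56. Assume that the interim estimate is the true effect (observed trend) and that half the information is in. Then

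conditional power = 1 − Φ[(1.08968 − 1.41421 × Z1) / 0.70711].

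| Interim difference (letters) | Z1 | Conditional power, observed trend |
|---|---|---|
| 0 | 0 | 6% |
| 1.75 | 0.68 | 43% |
| 3.5 | 1.37 | 88% |

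**3. What is still open at the look.**

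- Week 12 data: 96 − 44 = 52 randomized subjects without a counted value, less those who have discontinued.
- Deviations: the only stated deadline is before unmasking. Some may be unclassified at the interim.
- Primary imputation: named in Section 10.6.3, not specified. No date is given for a final SAP relative to the interim cut.
- Termination: open under Section 8.7.

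**4. Whether enrolment is still open.** Assume all 13 sites start together.

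- Rate: 13 × 2 = 26 to 13 × 5 = 65 per month.
- Enrolment ends at 96/65 = 1.5 to 96/26 = 3.7 months.
- The 44th Week 12 visit comes no earlier than 44/65 + 2.76 = 3.4 to 44/26 + 2.76 = 4.5 months, taking 12 weeks as 2.76 months.
- Enrolment would still be running at the look only if 52/rate exceeded 2.76 months, that is, below about 19 per month.

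At the planned rates, who is enrolled is therefore mostly not exposed. The handling of subjects already enrolled is.

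**The case against.** The strongest reply is that the permission is narrow. The independent biostatistician still runs the analysis, individual codes stay restricted, and the examining ophthalmologist is masked (Section 8.3). One person sees group summaries, and the documents do not say that this person is an employee of the sponsor or works on the trial. Group means identify no subject's arm, so steering deviation classification would be hard. A Phase IIb sponsor may also have a legitimate planning use for the results. All of this stands. It limits the point to a risk that the plan leaves uncontrolled, and it makes outright deletion of the sentence unnecessary. It does not supply the missing purpose or separation.

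A reader might infer more than the documents support:

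- **That independence is undone or the result biased.** Neither is shown. The safeguard is weakened.
- **That the whole second half of the trial is exposed.** At the Section 5.1 rates, enrolment is probably complete by the look.
- **That the primary imputation model is deferred to a later SAP.** The phrase "will be detailed in the formal statistical analysis plan" in Section 10.6.4 concerns missing VFQ-25 item scores only. What can be said is that Section 10.6.3 leaves the primary model unspecified and that the timing of the SAP is not stated.
- **That the false-positive rate is inflated by the possibility of stopping.** The boundary covers an early superiority claim, and stopping for poor results does not raise it.
- **That the summaries settle the outcome.** If the design effect of 3.5 letters is assumed for the remaining data, the same three interim differences give 43%, 69% and 88%, against 80.6% beforehand. That shift is much smaller. The wider range in the working depends on the observed-trend assumption, and the interim estimate itself has a standard error of 2.56 letters.

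**Conclusion.** The point holds as a conflict within Section 10.4: the section protects against operational bias, then allows arm-level disclosure to a sponsor appointee with no purpose, decision or firewall attached. It is correct that no action is tied to the look, although a formal test with an efficacy boundary is specified and alpha is spent on it.

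The risk falls on the follow-up of about 52 subjects, deviation classification, analysis choices and termination. It is possible and uncontrolled, not demonstrated. How informative the summaries are depends on the SD of 8, half the information at the look and the observed-trend assumption. The view that enrolment would be closed depends on the planned rates and a common site start. The plan should be changed before the interim data cut. Nothing here faults its alpha, power or sample size.

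**What to change.** In Section 10.4, choose one of two wordings:

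1. Before database lock, release outside the unmasked statistical team only whether the efficacy boundary was crossed. This discloses far less: with the planned figures, not crossed means only that the difference was below 1.73051 × 2.56 = 4.43 letters.
2. If the summaries are kept for planning, state that purpose. State also that until lock the recipient has no part in site contact, data review, deviation classification, the SAP or the analysis.

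Under either wording, require the SAP, including the primary imputation model and the per-protocol rules, to be final before the interim data cut.

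The cost is one or two sentences, earlier SAP sign-off, and restricted sponsor use of arm-level data for a few months. It needs no more subjects and changes neither alpha nor power.

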### **10.5 Study Populations**

*ITT Population:* The intent-to-treat (ITT) population will consist of all randomized subjects, analyzing subjects under the treatment to which they were randomized.

*PP Population:* The per-protocol (PP) population is a subset of the ITT population and includes subjects who do not deviate from the protocol in any way likely to seriously affect the primary outcome of the study, analyzing subjects under the treatment actually received. Important protocol deviations related to study inclusion or exclusion criteria,

conduct of the trial, subject management, or subject assessment will be identified prior to unmasking treatment.

*Safety Population:* The safety population includes all randomized subjects who receive at least one dose of study medication. The safety population will be analyzed as treated and will be used for the safety analyses. No data will be excluded for any reason.

## 10.6 Statistical Analysis

### 10.6.1 Methods of Analysis

Summaries for continuous variables will include the sample size, mean, standard deviation, median, minimum, and maximum. Summaries for discrete variables will include frequencies and percentages. Differences between treatment groups will be calculated as DexNP – Vehicle and change from baseline will be calculated as follow-up visit – baseline. The baseline visit will be defined as the last non-missing measure prior to initiation of investigational treatment. All efficacy analyses will use a one-sided alpha = 0.15 test unless otherwise stated.

All summaries will be presented by treatment group and where appropriate by visit.

### 10.6.2 Subject Demographics and Baseline Characteristics

Continuous summary statistics will be presented for the quantitative variable age (years), by treatment group and for all subjects. Discrete summary statistics will be generated for qualitative demographic variables: age category, gender, ethnicity, race, and iris color for the study eye, tabulated by treatment group and for all subjects.

Medical history will be coded using Medical Dictionary for Regulatory Activities (MedDRA®). Medical history will be summarized using discrete summary statistics for each MedDRA® system organ class (SOC) and preferred term (PT) by treatment group and for all subjects. Medical history will be presented separately for ocular and non-ocular histories. Subjects with multiple medical histories in the same SOC or PT will be counted only once for that respective SOC or PT.

